8.5. Recording and Reporting of Adverse Event

All Liver graft-related adverse events and serious adverse events are to be recorded on the electronic case report forms until post-transplant day 30 or until initial hospital discharge, whichever comes first. The description of the adverse event will include: the date of onset, duration, severity, seriousness, the relationship of the event to the trial treatment, anticipated or not, and any treatment required. All serious adverse events occurring during the course of the first 30 days post-transplant will be reported to TransMedics, Inc., as well as documented on the appropriate electronic case report form(s). For all SAEs, the investigator is required to supply any additional data that may be deemed necessary by the Sponsor. Additionally any serious adverse events (SAE) and unanticipated adverse device effects (UADE) should be reported to TransMedics, Inc., preferably within 48 hours of the time the investigator learns of the event, but in no case later than 5 working days. Liver graft-related AEs will be recorded up to the 30-day follow-up or through hospital discharge only if longer than 30 days. For any particular patient, the Independent Medical Monitor if required to protect patient safety may specify a different follow-up period. The Sponsor is responsible for the classification and reporting of Liver graft-related adverse events to the appropriate regulatory authorities, and for the on-going safety evaluation of the trial in accordance with ISO 14155 and governing regulatory requirements.

8.6. Relationship of an Adverse Events to OCSTTM Liver (OCS) or Standard of Care (Control)

The investigator will assess the relationship of the AE to the OCS or Control methods of preservation. The relationship will be assessed using the following categories:

- **Definitely Related:** There is a reasonable causal and temporal relationship between preservation with the OCSTTM Liver and the adverse event.
- **Probably Related:** It is more likely than not that there is a reasonable causal relationship between preservation with the OCSTTM Liver and the adverse event.
- **Possibly Related:** There is a reasonable relationship with preservation with the OCSTTM Liver and the adverse event, but the causal relationship is unclear or lacking.

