- **Unlikely Related:** There is a temporal relationship with preservation with the OCSTTM Liver and the adverse event, but there is not a reasonable causal relationship between the trial device and the event.
- **Unrelated:** There is no relationship between preservation with the OCSTTM Liver and the adverse event.

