In addition, the numbers and percentages of subjects experiencing at least one treatment-emergent adverse event (TEAE) in the following categories will be tabulated by treatment group: liver graft-related TEAEs, treatment-related (definitely or probably-related) TEAEs, serious TEAEs, and serious liver graft-related TEAEs. The number of treatment-emergent liver graft-related adverse events, treatment-emergent serious adverse events (within 30 days post-

transplant and overall), treatment-emergent serious liver graft-related adverse events (within 30 days post-transplant and overall), treatment-emergent adverse events resulting in study discontinuation, and treatment-emergent serious adverse events with an outcome of death (within 30 days post-transplant and overall) will be tabulated by system organ class and preferred term using MedDRA (Version 13.0 or higher). Liver graft-related TEAEs and liver graft-related serious TEAEs will also be tabulated at the event level by system organ class and preferred term and the relationship of the liver graft-related adverse event to the investigational treatment using counts and percentages. Similar analyses at the event level will be performed by the severity of the adverse event.

The adverse event analyses above will also be presented by subgroup.

An exploratory analysis of the frequency of non-ischemic biliary complications through 30 days post-liver transplantation per subject will be performed. This endpoint will be summarized by treatment group using descriptive statistics. For each treatment group, a 95% confidence interval for the mean based on the t-distribution will be presented. Also, a 95% confidence interval based on the t-distribution will be presented for the difference in means between the two treatments.

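### Adverse-event relatedness is to be judged in both arms, but all five categories are worded for OCS only, so the by-arm count of related events is not interpretable as written

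*Protocol*

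**What the plan says.** The heading of Protocol 8.6 names both OCS and Control, and its first sentence sets the scope: "The investigator will assess the relationship of the AE to the OCS or Control methods of preservation".

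The five definitions that follow are narrower. Probably Related begins "It is more likely than not that there is a reasonable causal relationship between preservation with the" and goes on to name the OCS Liver. Unrelated begins "There is no relationship between preservation with the" and names the OCS Liver again. Definitely and Possibly Related do the same. Unlikely Related also refers to the device itself: "there is not a reasonable causal relationship between the trial device and the event".

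The rating feeds several outputs:

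- Protocol 9.4 counts subjects with a device-related event (definitely or probably) by treatment group, and tabulates events by relationship to the device.
- SAP 13 makes the same cut under another name, "treatment-related (definitely or probably-related) TEAEs", also by treatment group.
- SAP 13 and Table 3.3.6.1 tabulate liver graft-related events by relationship to the investigational treatment.

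SAP 13 bases adverse-event analyses on CEC-adjudicated events. Neither document states a causality scale for the CEC.

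**The concern.** A percentage of subjects with treatment-related events, shown side by side for two arms, reads as if each arm had been judged against its own treatment. That needs a definition that works in both arms. Here the definition works only for livers that were on OCS.

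The gap matters because harm from cold storage is part of the trial's rationale: Protocol 1.1 links time-dependent ischaemic injury under cold storage to complications after transplant. A scale with no category for a relationship to cold storage cannot record that. On the literal reading the table makes OCS look worse than Control by construction. On a looser reading the Control count depends on how each rater filled the gap. The trial is unblinded (SAP 3.3), so raters can know which method was used and either practice is possible.

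**Working it through.** The plan gives no figure to reproduce, so the check compares the texts and adds one line of illustrative arithmetic.

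**Step 1. Scope against definitions (Protocol 8.6).**

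| Element | Refers to |
|---|---|
| Section heading | OCS or Control |
| First sentence | OCS or Control |
| Definitely Related | OCS Liver only |
| Probably Related | OCS Liver only |
| Possibly Related | OCS Liver only |
| Unlikely Related | OCS Liver, and the trial device |
| Unrelated | OCS Liver only |

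No category names cold storage or uses a neutral term such as the method the liver received.

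**Step 2. Can a Control liver in the safety tables have had OCS exposure?** SAP 6.3 classifies a liver as OCS if it was preserved on OCS at any time. A liver counted as Control therefore had none. On the literal wording, the only category that fits a Control event is Unrelated.

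**Step 3. Is there a repair elsewhere?**

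- Protocol 8.5 asks for the relationship to the trial treatment, without defining it for Control.
- Protocol 14.9 words the Medical Monitor's classification as relatedness to the device.
- SAP 13 relies on CEC adjudication but gives no scale.
- SAP 3.5, which lists changes from the protocol, does not mention relatedness.
- The draft case report forms (Protocol Appendix 4) are blank in this copy, so the wording on the form is not known.

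**Step 4. What the table would show.** Let p be the true proportion of Control recipients with an event definitely or probably related to their preservation method. On the literal reading the table shows 0 for Control, so the error in the between-arm difference is p − 0 = p. The documents give no value for p. With 300 transplanted subjects randomised 1:1, each arm has about 300 / 2 = 150. If p is the same in both arms (assumption):

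| Assumed p | OCS shown | Control shown | False difference |
|---|---|---|---|
| 5% | 7.5 of 150 | 0 of 150 | 5 points |
| 10% | 15 of 150 | 0 of 150 | 10 points |
| 20% | 30 of 150 | 0 of 150 | 20 points |

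This arithmetic only returns the assumed rate. It shows that the error is as large as the quantity the Control column is meant to show. It does not estimate what the trial would find.

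**Step 5. Which analyses use the scale?**

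- *Affected:* the related-event row by treatment group and the event-level relationship tables. These are counts and percentages, with no planned test.
- *Not affected:* the principal safety endpoint, liver graft-related SAEs to day 30. Protocol 8.1 defines graft-related by the function of the transplanted liver, and the endpoint counts four named event types (SAP 13).
- *Not affected:* ischaemic biliary complications within 6 and 12 months (SAP 14), which are counted in both arms whatever their relatedness rating.

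**The case against.** The strongest reply is that the first sentence of Protocol 8.6 governs. A rater who reads cold storage in place of the OCS Liver for a Control event is doing what that sentence asks, so the documents do not require a zero. This stands. It rules out the claim that Control events cannot be rated, but it does not supply a definition. The substitution is unwritten, and nothing ensures that all raters make it.

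A reader might also infer that the SAP turned a one-arm device item into a two-arm comparison. The documents do not support that. Protocol 9.4 already tabulates device-related events by treatment group, and Protocol 8.5 already speaks of trial treatment. What is new in SAP 13 is the label treatment-related, which makes a Control zero harder to recognise as a product of the definition.

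Table 3.3.6.1 is titled by relationship to the investigational treatment. Since that treatment is OCS, the title fits the wording of 8.6. This also stands: the table does not claim to show which method causes more events, but a Control column in it would carry no information on the literal reading.

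Finally, one cannot say that the CEC used the defective wording. The documents show only that its scale is not stated.

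**Conclusion.** The inconsistency is in the current text and can be confirmed by reading Protocol 8.6. As written, the by-arm tabulation of definitely or probably related events has no common definition and is not interpretable between arms. On the literal reading Control is zero, and the false difference equals the true Control rate, which is unknown. If raters substitute cold storage, the size of any distortion depends on how consistently they do so.

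A reader might go further and conclude that the safety comparison as a whole is invalid, or that the trial cannot say which arm has more graft complications. The documents do not support that. The affected outputs are descriptive, and the formal safety test and the ischaemic biliary comparison do not use the scale. The point is worth correcting because it is cheap to fix and the table is easily misread, but no tested endpoint is at risk.

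**What to change.** 1. In Protocol 8.6, define all five categories by the preservation method the liver received (OCS or cold storage), and change the reference to the trial device in Unlikely Related in the same way.
2. State in SAP 13 that the CEC applies this wording to all adjudicated events in both arms. Re-rating Control events alone would add a new asymmetry, and leaving earlier events on the old wording would mix two scales.
3. Keep a separate item for relatedness to the OCS device, reported for OCS livers only.
4. If events will not be re-rated on a common scale, show the treatment-related row in SAP 13 and Table 3.3.6.1 for the OCS arm only, labelled as relatedness to OCS, with no between-arm comparison.
5. Align the terms device-related, treatment-related and investigational treatment across both documents, and record the change in SAP 3.5.

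The cost of the first route (items 1 to 3) is a wording amendment and CEC time to re-rate events in both arms. The cost of item 4 is a change to the SAP tables and the loss of a descriptive Control column.

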8.7. Severity

The investigator will rate the severity of the adverse event using the following categories:

- **Mild:** The adverse event is transient and/or easily tolerated by the subject.
- **Moderate:** The adverse event causes the subject discomfort and interrupts the subject's usual activities.
- **Severe:** The adverse event causes considerable interference with the subject's usual activities.

8.8. Pre-Existing Conditions

Pre-existing diseases or conditions will not be reported as adverse events.

9. STATISTICAL METHODS

9.1. General

Continuous variables will be summarized using descriptive statistics, specifically the mean, median, standard deviation, minimum, and maximum. Categorical variables will be summarized using frequencies and percentages.

9.2. Analysis Populations

9.2.1. Per Protocol Population

The Per Protocol (PP) Population will consist of all randomized subjects who are transplanted and have no major protocol violations and for whom the donor liver received the complete preservation procedure as per the randomization assignment. The major protocol violations that will exclude a subject from this population are the following:

- Ineligible for the study according to the recipient inclusion and exclusion criteria
- Ineligible for the study according to the donor organ inclusion and exclusion criteria
- Subject is transplanted with a liver with preservation other than that to which the subject was randomized
- Failure to complete adequate post-transplant assessments to support the primary, secondary or safety endpoints
- Other major protocol violations

In analyses based on the PP Population, subjects will be analyzed as randomized. The primary analysis of effectiveness and of secondary and other endpoints will be based on the PP Population.

9.2.2. Modified Intent-to-Treat Population

The Modified Intent-to-Treat Population (mITT) will consist of all randomized subjects who are transplanted. In analyses based on mITT Population, subjects will be analyzed as randomized. The mITT analyses will be considered secondary analyses of effectiveness.

9.2.3. As Treated Population

The As Treated Population (AT) will consist of all treated subjects, i.e., all subjects who are transplanted in the study with a donor liver preserved with either OCS or Control. In analyses based on this population, subjects will be analyzed as treated. A subject who receives a liver with some preservation with OCS and some with standard of care will be analyzed according to the initial preservation. After the initiation of preservation, any switchover in preservation method should be recorded as a protocol deviation and those subjects will not be considered part of the AT population. Analyses of safety endpoints will be performed based on the AT Population

9.2.4. Donor Liver Population

The Donor Liver Population will consist of all donor livers for which the potential recipient was randomized and which have preservation initiated using OCS or Control. In some of the analyses based on this population, livers will be analyzed as randomized; in others, they will be analyzed as treated. For the analyses based on the actual treatment of the liver, a liver with some preservation with OCS and some with standard of care will be analyzed according to the initial preservation.

9.3. Analysis of Effectiveness Endpoints

9.3.1. Primary Effectiveness Endpoint

The primary effectiveness endpoint for this study is Early Liver Allograft Dysfunction (EAD), defined as presentation of one or more of the following criteria:

- AST level >2000 IU/ml within the first 7 postoperative days;
- Bilirubin ≥ 10 mg/dl on postoperative day 7;
- INR ≥ 1.6 on postoperative day 7; or
- Primary non-functioning graft within the first 7 days

The primary hypothesis for this study is that the OCS treatment is non-inferior to the standard of care treatment with respect to this endpoint. The primary statistical hypotheses are as follows:

$$H_{10}: \pi_{1,OCS} \geq \pi_{1,CONTROL} + \delta \text{ and}$$

$$H_{11}: \pi_{1,OCS} < \pi_{1,CONTROL} + \delta,$$

where $\pi_{1,OCS}$ and $\pi_{1,CONTROL}$ are the true proportions of subjects with Early Liver Allograft Dysfunction for the OCS and standard of care treatments, respectively, and δ is the non-inferiority margin which is here taken to be 0.075. If non-inferiority is demonstrated using a significance level of 0.05, a two-sided test of superiority will be performed.

The primary effectiveness endpoint will be analyzed by calculating, for each treatment group, the sample proportion of subjects meeting the primary effectiveness endpoint, as well as an exact (Clopper-Pearson) 95% confidence interval for the corresponding population proportion. The 95% upper bound of the exact unconditional one-sided confidence interval based on the Farrington and Manning score statistic¹⁸ will be calculated for the difference between the two population proportions ($\pi_{1,OCS} - \pi_{1,CONTROL}$). An upper confidence limit less than $\delta = 0.075$ will result in rejection of the null hypothesis (H_{10}) in favor of the alternative hypothesis (H_{11}) and the

demonstration of non-inferiority of OCS to control for the primary effectiveness endpoint. In the event non-inferiority is demonstrated, Fisher's exact test (two-sided) will be used to test for superiority.

This endpoint will be analyzed using the Per Protocol and mITT Populations. The Per Protocol analysis will be considered the primary analysis. Multiple imputation methods will be used for data imputation for any patients with missing values for this endpoint.

Subgroup analyses of the primary effectiveness endpoint will be performed for the following subgroups of patients:

- DCD (donation after circulatory death) patients
- Fatty liver patients
- Other liver patients

No data imputation or statistical tests will be performed for these subgroup analyses.

9.3.2. Secondary Effectiveness and OCS Donor Liver Assessment Endpoints

The secondary effectiveness endpoints for this trial are as follows:

- OCS Measurements during organ perfusion
- Patient survival at day-30 post-transplantation
- Patient survival at time of initial hospital discharge post-transplantation

The null and alternative hypotheses for the endpoint of OCS donor liver assessment during perfusion are:

$$H_0: \pi_3 \leq 0.85 \text{ and}$$

$$H_1: \pi_3 > 0.85,$$

respectively, where π_3 is the true proportion of livers, among donor livers preserved using OCS for the entire preservation period, on which measurements of lactate level, average bile production rate, Hepatic Artery and Portal Vein Pressure during perfusion will be available on OCS device before transplant.

This secondary endpoint on OCS liver assessment during organ perfusion will be analyzed by calculating the sample proportion of donor livers placed on OCS meeting this secondary endpoint, as well as an exact (Clopper-Pearson) 95% one-sided lower confidence bound for the corresponding population proportion. A lower confidence bound greater than 0.85 will result in rejection of the null hypothesis in favor of the alternative hypothesis and the demonstration that the true proportion is greater than 0.85 for the OCS donor liver assessment endpoint.

Each secondary effectiveness endpoint will be summarized using counts and percentages and an exact 95% confidence interval for the true percentage based on the binomial distribution. The secondary effectiveness endpoints will be analyzed using the PP Population.

The statistical hypotheses for the first secondary effectiveness endpoint, patient survival at day-30 post-transplantation, are as follows:

$$H_{20}: \pi_{2,OCS} \leq \pi_{2,CONTROL} - \delta \text{ and}$$

$$H_{21}: \pi_{2,OCS} > \pi_{2,CONTROL} - \delta,$$

where $\pi_{2,OCS}$ and $\pi_{2,CONTROL}$ are the true proportions of the subjects surviving to day-30 post-transplantation for the OCS and standard of care treatments, respectively, and δ is the non-inferiority margin, which is here taken to be 0.075. This endpoint will be analyzed by calculating the 95% upper confidence limit based on the normal approximation for the difference between the two population proportions ($\pi_{2,CONTROL} - \pi_{2,OCS}$). An upper confidence limit less than $\delta = 0.075$ will result in rejection of the null hypothesis (H_{20}) in favor of the alternative hypothesis (H_{21}) and demonstration of non-inferiority of OCS to Control. In the event non-inferiority is demonstrated, Fisher's exact test (two-sided) will be used to test for superiority.

The second secondary effectiveness endpoint, patient survival at initial hospital discharge post liver transplantation, will be analyzed in a manner analogous to the first secondary effectiveness endpoint with the same non-inferiority margin of 0.075.

Because fixed sequence testing will be used for the secondary endpoints, no adjustment for the multiplicity of these endpoints needs to be made. The endpoints will be tested in the order listed above. The test for non-inferiority for the first secondary effectiveness endpoint will be performed only if the null hypothesis has been rejected for the OCS donor liver assessment endpoint. The test for non-inferiority for the second secondary effectiveness endpoint will be performed only if the null hypothesis has been rejected in favor of the alternative hypothesis of non-inferiority of the OCS treatment to the Control treatment for the first secondary effectiveness endpoints. Similarly, the test for superiority for the second secondary effectiveness endpoint will be performed only if the null hypothesis of equality has been rejected in favor of superiority of the OCS treatment to the Control treatment for the first secondary effectiveness endpoints (and non-inferiority has been demonstrated for the given secondary effectiveness endpoint). Due to statistical power limitations, it is not expected that non-inferiority will be demonstrated for patient survival at day 30 or at initial hospital discharge.

These endpoints will be analyzed using the Per Protocol and mITT Populations, with the Per Protocol analysis being considered the primary analysis. Multiple imputation methods will be used for data imputation for patients with missing values for these endpoints.

Subgroup analyses of the secondary endpoints will be performed for the same subgroups of patients as for the primary effectiveness endpoint. No data imputation or statistical tests will be performed for these subgroup analyses.

9.4. Analysis of Safety

Safety will be analyzed principally by examination of the frequency of liver graft-related serious adverse events (SAEs) up to the 30-day follow-up after transplantation. This endpoint is defined as the average number of liver graft-related serious adverse events through the 30 days post-liver transplantation per subject, consisting of the following serious adverse events (at most one per type per person):

- Primary non-function (defined as irreversible graft dysfunction requiring emergency liver re-transplantation or death with the first 10 days, in the absence of immunologic or surgical causes);
- Ischemic biliary complications (ischemic biliary strictures, and non-anastomotic bile duct leaks);

- Vascular complications (Liver graft-related coagulopathy, hepatic artery stenosis, hepatic artery thrombosis and portal vein thrombosis);
- Liver allograft infections (liver abscess, cholangitis, etc.)

This endpoint will be summarized by treatment group using descriptive statistics. For each treatment group, a 95% confidence interval for the mean based on the t-distribution will be presented. Also, a 95% confidence interval based on the t-distribution will be presented for the difference in means between the two treatments.

For the number of liver graft-related SAEs, the statistical hypotheses are as follows:

$$H_{30}: \mu_{OCS} \geq \mu_{CONTROL} + \delta \text{ and}$$

$$H_{31}: \mu_{OCS} < \mu_{CONTROL} + \delta,$$

where μ_{OCS} and $\mu_{CONTROL}$ are the true mean numbers of liver graft-related SAEs up to the 30-day follow-up after transplantation per subject with the OCS and standard of care treatments, respectively, and δ is the non-inferiority margin, which is here taken to be 1.00. The safety endpoint will be analyzed using a one-sided, two-sample t-test with an alpha level of 0.05. If non-inferiority is demonstrated, a corresponding (two-sided) test of superiority will be performed.

This endpoint will be analyzed based on the As Treated Population.

In addition, the numbers and percentages of subjects experiencing at least one liver graft-related AE, at least one (definitely or probably-related) device-related AE, at least one unanticipated AE, and at least one serious AE, and the number and percentage of deaths will all be tabulated by treatment group. Also, the number of liver graft-related adverse events and the number and percentage of subjects experiencing liver graft-related adverse events will be tabulated by system organ class and preferred term using MedDRA. A similar analysis will be performed for liver graft-related SAEs. AEs will also be tabulated at the event level by system organ class and preferred term and the relationship of the adverse event to the device using counts and percentages. Similar analyses will be performed by the severity of the adverse event.

The numbers and percentages of donor livers in the Donor Liver Population that are treated as randomized and transplanted, treated not as randomized and transplanted, treated as randomized and not transplanted, and treated not as randomized and not transplanted will be presented. For livers that are treated not as randomized, the reason will also be summarized using counts and percentages. Both of these analyses will be done based on the randomized treatment for the liver, but the following analyses will be based on the actual treatment of the liver. For livers that are not transplanted, the reason(s) for non-transplantation (including device failure) will be summarized using counts and percentages. The number and percentage of donor livers in the Donor Liver Population for which there was a device failure will also be presented.

